7.11 Arm A Regorafenib Dose Escalation

Cycle 1:

Week	Dose
1 Starting Dose	80 mg*
2	120 mg
3	160 mg
4	Off

*starting dose level

Cycle 2 and beyond:

Week	Dose
1	Remain at highest tolerated dose from Cycle 1 (up to 160 mg)
2	
3	
4	Off

7.12 Arm B Regorafenib Dose (all cycles)

Week	Dose
1 Starting Dose	160 mg
2	
3	
4	Off

- 7.2 Patients can be instructed in administration techniques and granted treatment independence with nursing staff approval.
- 7.3 For this protocol, the patient must return to the consenting ACCRU institution for evaluation at least every 7 days during treatment and every 28 days during active monitoring.
- 7.4 Treatment by a local medical doctor (LMD) is not allowed.

8.0 Dosage Modification Based on Adverse Events

Strictly follow the modifications in the following tables for the first **two** cycles, until individual treatment tolerance can be ascertained. Thereafter, these modifications should be regarded as guidelines to produce mild-to-moderate, but not debilitating, side effects. If multiple adverse events are seen, administer dose based on greatest reduction required for any single adverse event observed. Reductions or increases apply to treatment given in the preceding cycle and are based on adverse events observed since the prior dose.

ALERT: *ADR reporting may be required for some adverse events (See Section 10)*

8.1 Arm A Regorafenib Dose Escalation/Reduction

Dose level	If No SDRT	If + SDRT**
80 mg*	Proceed to next dose level	-
120 mg	Proceed to next dose level	Decrease to 80 mg
160 mg	-	Decrease to 120 mg

*starting dose level

**SDRT = Significant Drug Related Toxicities

- 8.11 After week 8, if toxicities have resolved to \leq Grade 0-1, re-escalation is allowed 40 mg at a time every 4 weeks to a maximum of 160 mg and at the discretion of the treating investigator.
- 8.12 Patients with dose reductions below 80 mg should go off treatment and go to event monitoring.
- 8.13 Any patients with toxicities requiring >4 week delay should go off treatment and then to event monitoring.

Regorafenib may be dose reduced per the table in Section 8.2 in case of intolerable toxicity such as weight loss, fatigue, rash or anorexia.

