1.0 Background

- 1.1 Worldwide, nearly 1.3 million patients are diagnosed with and more than 600 000 patients die from colorectal cancer every year (Ferlay et al, 2013). Regorafenib is a novel oral multikinase inhibitor that blocks the activity of several protein kinases, including kinases involved in angiogenesis, oncogenesis and tumor microenvironment (Kies et al, 2010). Regorafenib was recently shown to provide a survival benefit in metastatic colorectal cancer patients who have progressed after all standard therapies (Grothey, et al). This led to its approval in September 2012 by the FDA for use in the United States. Despite the observed benefits in a patient population with no current standard, toxicities such as Palmar-plantar erythrodysesthesia syndrome (PPES) (which occurs early in the first 1-2 weeks) and fatigue have widely limited its use in the US. Multiple practices across the US have adopted, and despite the absence of supportive data, various dosing or interval scheduling including starting at lower doses and escalate as tolerated, every other week dosing intervals and other.

In this study, we propose to design a novel strategy to optimize the dose of regorafenib in patients with refractory mCRC to allow maintenance of the observed benefits while improving the tolerability profile. The proposed strategy, arm A (combining A1 and A2) consists of starting regorafenib at 80 mg/day for 1 week (week1), then if no significant drug-related toxicities escalate to 120 mg/ day for another week (week 2), then again if no significant related toxicities escalate to a total dose of 160 mg/day (week 3) followed by a week break (week 4 of cycle 1). If at the end of week 1, week 2 or week 3 toxicities are unacceptable as defined by the study, the decision will be to deescalate by 40 mg/day and there will be no further dose escalations. A comparative arm, arm B (combining B1 and B2) will include a standard dose/schedule regorafenib of a 160 mg/day starting on day 1 of cycle 1. The primary goal of this study is to compare the proportions of patients on each arm who complete 2 cycles of protocol treatment and initiate cycle 3. We will also assess other outcome and quality of life measures and toxicity profile with a focus on regorafenib related toxicities. We will also assess a potential strategy to reduce the severity of PPES. Additionally, we will perform limited PK analysis in both arms.

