8.2 Arm B Regorafenib Dose Levels (Based on Adverse Events in **Tables 8.3.**)

Dose Level	Drug	Dose
0*	Regorafenib	160 mg daily, Four 40-mg tablets
-1	Regorafenib	120 mg daily, Three 40-mg tablets
-2	Regorafenib	80 mg daily, Two 40-mg tablets

* Dose level 0 refers to the starting dose.

- 8.21 After week 8, if toxicities have resolved to \leq Grade 0-1, re-escalation is allowed 40 mg at a time every 4 weeks to a maximum of 160 mg and at the discretion of the treating investigator.

- 8.22 Patients with dose reductions below 80 mg should go off treatment and go to event monitoring.

If a subject experiences more than one toxicity, dose reduction should be according to the toxicity with the highest grade.

In the case of two or more toxicities of the same grade, the investigator may dose reduce according to that deemed most causally related to study treatment.

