Further description / examples of skin changes	Numbness, dysesthesia / paresthesia tingling, painless swelling, or erythema of the hands and/or feet	Painful erythema and swelling of the hands and/or feet	Moist desquamation, ulceration, blistering, or severe pain of the hands and/or feet
Effect on activities	Does not disrupt normal activities	Limiting instrumental activities of daily life (e.g., preparing meals, shopping for groceries or clothes, using the telephone, managing money)	Limiting self-care activities of daily life (e.g., bathing, dressing and undressing, feeding self, using the toilet, taking medications) and not bedridden
a. Palmer-plantar erythrodysesthesia syndrome is a disorder characterized by redness, marked discomfort, swelling, and tingling in the palms of hands or the soles of the feet.			

Grade of event (NCI-CTCAE v4.0)	Occurrence	Suggested Dose Modification
Grade 1	Any	Maintain dose level and immediately institute supportive measures for symptomatic relief
Grade 2	1 st occurrence	Consider decreasing dose by one dose level and immediately institute supportive measures. If no improvement, interrupt therapy for a minimum of 7 days, until toxicity resolves to Grade 0-1 ^{b,d}
	No improvement within 7 days or 2 nd occurrence	Interrupt therapy until toxicity resolves to Grade 0-1. When resuming treatment, treat at reduced dose level ^b
	3 rd occurrence	Interrupt therapy until toxicity resolves to Grade 0-1. When resuming treatment, decrease dose by one dose level. ^{b,d}
	4 th occurrence	Discontinue therapy
Grade 3	1 st occurrence	Institute supportive measures immediately. Interrupt therapy for a minimum of 7 days until toxicity resolves to Grade 0-1. ^c When resuming treatment, decrease dose by one dose level. ^{b,d}
	2 nd occurrence	Institute supportive measures immediately. Interrupt therapy for a minimum of 7 days until toxicity resolves to Grade 0-1. ^c When resuming treatment, decrease dose by one additional dose level. ^{b,d}
	3 rd occurrence	Discontinue treatment permanently.

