8.34 Hypertension

Hypertension is a known AE associated with regorafenib treatment. Subject will have their blood pressure measured at least weekly during the first 5 weeks of treatment. If additional blood pressure measurements are done outside the study site, and the blood pressure is >140 mm Hg systolic or >90 mm Hg diastolic (NCI CTCAE v4.0), then the subject must contact study personnel. The management of hypertension, including the choice of antihypertensive medication, will be performed according to local standards and to the usual practice of the investigator. Every effort should be made to control blood pressure by medical means other than study drug dose modification. If necessary, Tables Section 8.1 and 8.2 outline suggested dose reductions.

Table 8.34: Management of Treatment-Emergent Hypertension		
Grade (CTCAE v4.0)	Antihypertensive Therapy	Regorafenib Dosing
1 Prehypertension (systolic BP 120 - 139 mmHg or diastolic BP 80 - 89 mmHg)	None	Continue regorafenib Consider increasing blood pressure (BP) monitoring
2 Systolic BP 140 - 159 mmHg or diastolic BP 90 - 99 mmHg, OR Symptomatic increase by >20 mmHg (diastolic) if previously within normal limits	Treat with the aim to achieve diastolic BP \leq 90 mm Hg: If BP previously within normal limits, start anti-hypertensive monotherapy If patient already on anti-hypertensive medication, titrate up the dose.	Continue regorafenib If symptomatic, hold regorafenib until symptoms resolve AND diastolic BP \leq 90 mm Hg ^a . When regorafenib is restarted, continue at the same dose level.
3 Systolic BP \geq 160 mmHg or diastolic BP \geq 100 mmHg OR More than one drug or more intensive therapy than previously used indicated	Treat with the aim to achieve diastolic BP \leq 90 mm Hg: Start anti-hypertensive medication AND/OR Increase current anti-hypertensive medication AND/OR Add additional anti-hypertensive medications.	Hold regorafenib until diastolic BP \leq 90 mm Hg, and if symptomatic, until symptoms resolve ^a When regorafenib is restarted, continue at the same dose level. If BP is not controlled with the addition of new or more intensive therapy, reduce by 1 dose level. If Grade 3 hypertension recurs despite dose reduction and antihypertensive therapy, reduce another dose level.
4 Life-threatening consequences (e.g., malignant hypertension, transient or permanent neurologic deficit, hypertensive crisis)	Per institutional guidelines	Discontinue therapy

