16.3 Statement for Primary Endpoint

The primary endpoint is the proportion of patients in each arm who complete 2 cycles of protocol treatment and initiate cycle 3. The proportion will be calculated among evaluable patients separately by arm (Arm A vs. Arm B). Evaluable patients are defined as patients who are eligible, consented, received any protocol treatment. In the CORRECT trial, among patients who were randomized to regorafenib, 45% continued treatment beyond cycle 2. Other than disease progression, majority of patients discontinued regorafenib due to adverse events not associated with progression. It was noted that most adverse events occurred during Cycles 1-2 of the treatment (Grothey A et. al., 2013, Lancet). Assuming 45% of patients would complete 2 cycles of protocol treatment and initiate cycle 3 in the control (standard dose; pooled arms B1 and B2) group, and desiring an improvement to 63% in the experimental (starting low dose) group (pooled arms A1 and A2), a one-sided test with $\alpha = 0.20$ and power of 80% will require a sample size of 110 patients enrolled to both regorafenib arms (A and B). We will enroll 13 additional patients to account for ineligibility, cancellation, major treatment violation, or other reasons. Maximum projected accrual is therefore 123 patients. A Fisher exact test will be used to detect a difference in proportion of patients who complete 2 cycles of protocol treatment and initiate cycle 3 between arms (starting low dose [pooled arm A1 and A2] vs. standard dose [pooled arm B1 and B2]). The proportion of patients who complete 2 cycles of protocol treatment and initiate cycle 3 will be computed by arm with its 95% confidence interval using exact method.

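### Section 8 gives conflicting dose-change instructions inside cycles 1-2, the primary endpoint window, and the Arm A trigger (SDRT) has no stated criterion

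*Combined protocol and SAP*

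**What the plan says.** Section 8.0 opens with "Strictly follow the modifications in the following tables for the first" two cycles; after that the tables become guidance. It names no arm.

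Section 8.1 covers Arm A. Its table lists three dose levels and, for each, an action without and with SDRT. The footnote reads "SDRT = Significant Drug Related Toxicities" and gives no grade, event or table row. Section 1.1 implies that a definition exists: if, at the end of week 1, 2 or 3, "toxicities are unacceptable as defined by the study, the decision will be to deescalate by 40 mg/day". Section 8.1 ends with "Regorafenib may be dose reduced per the table in Section 8.2 in case of intolerable toxicity such as weight loss, fatigue, rash or anorexia".

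Section 8.2 is headed "Arm B Regorafenib Dose Levels (Based on Adverse Events in" Tables 8.3, and holds the Arm B dose-level table.

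The tables in Section 8.3 name no arm. Table 8.31 covers toxicities other than PPES, hypertension and liver tests, and leaves the dose unchanged at Grade 0-2. The PPES table says for Grade 1: "Maintain dose level and immediately institute supportive measures for symptomatic relief". Table 8.34 says for Grade 3 hypertension, once pressure is controlled: "When regorafenib is restarted, continue at the same dose level". It reduces only if pressure stays uncontrolled on added therapy.

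Section 16.3 makes completing two cycles and starting cycle 3 the primary endpoint.

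**The concern.** Whether a patient starts cycle 3 depends partly on what is done about a poorly tolerated dose in cycles 1 and 2. In that same period 8.0 requires strict adherence to tables that cannot all be followed together.

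Three things are at stake. First, the experimental strategy: one event in Arm A can lead to escalation, no change or reduction, depending on which section a site reads first, so the strategy under test is not fixed. Second, the comparison: reduction practice could come to differ between arms in ways that nobody planned, and no blinding procedure is described that would limit this. Third, conduct: Section 13.2 classes a patient as a major violation on the basis of cycle 1 treatment, which is hard to judge when the rules disagree.

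**Working it through.** **Conflict 1: the ungraded trigger.** Take Grade 2 fatigue that the patient finds intolerable, in cycle 1.

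- Table 8.31: dose unchanged. Section 8.0: follow strictly.
- Closing sentence of 8.1: a reduction is permitted.
- Arm: by position the sentence belongs to Arm A; by its pointer to 8.2 it belongs to Arm B. If it covers both, it conflicts with Table 8.31 in both. If it covers one, the arms have different triggers. Either way the text needs reconciling.

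**Conflict 2: no outcome at 120 mg that keeps the dose.**

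| Event at 120 mg | 8.1 if not SDRT | 8.1 if SDRT | 8.3 tables |
|---|---|---|---|
| Grade 1 PPES | up to 160 mg | down to 80 mg | keep the dose |
| Grade 3 hypertension, then controlled | up to 160 mg | down to 80 mg | hold, then same dose |

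Read literally, neither column of 8.1 matches the 8.3 action. The conflict therefore remains however SDRT is defined. At 160 mg the non-SDRT cell is a dash, which can be read as staying, so a definition could settle matters there. At 120 mg it cannot.

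**Conflict 3: the 80 mg step.** Suppose that week 1 is not tolerated.

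- Section 1.1: go down by 40 mg/day; 80 - 40 = 40 mg/day.
- 8.1 table: the SDRT cell at 80 mg is a dash, which may mean stay or may mean no instruction.
- 8.12: a reduction below 80 mg takes the patient off treatment.

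One reading ends treatment, and so the chance of meeting the primary endpoint. The others do not.

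**Scale of the primary comparison.** Inputs from 16.3: "Assuming 45% of patients would complete 2 cycles of protocol treatment and initiate cycle 3 in the control" group, 63% in Arm A, one-sided alpha 0.20, power 80%, 110 patients, Fisher exact test.

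- Uncorrected n per arm = [z(0.80)·√(2 × 0.54 × 0.46) + z(0.80)·√(0.45 × 0.55 + 0.63 × 0.37)]² / 0.18² = 42.7, where 0.54 is the mean of the two rates.
- With continuity correction: (42.7/4) × [1 + √(1 + 4/(42.7 × 0.18))]² = 53.3, so 54 per arm and 108 in total.
- Exact enumeration of the one-sided Fisher test: power 79.7% at 54 per arm and 80.4% at 55 per arm. The plan's 110 is reproduced and is not in dispute.
- Target difference: 63 - 45 = 18 points; 0.18 × 55 = 9.9 patients per arm.

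**Illustration only.** The documents give no figure for the effect of differing reduction practice, so the shifts below are assumptions, shown in both directions. Same exact Fisher test, 55 versus 55, Arm B at 45%.

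| Assumed shift in the Arm A rate from reduction practice | No effect of the low start | True 18-point gain |
|---|---|---|
| None | 14.6% rejected | 80.4% power |
| +3 points | 23.1% | |
| +5 points | 30.0% | |
| +10 points | 50.1% | |
| -5 points | | 62.6% |
| -10 points | | 41.8% |

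Five points is 0.05 × 55 = 2.75, about three patients in Arm A. The table shows how sensitive the test would be to such a shift. It is not evidence that one occurs.

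**The case against.** The strongest reply is that this is loose drafting with a recoverable intent. SDRT may be meant to follow the 8.3 tables. Their instruction to keep the dose may mean only that the event does not call for a reduction, which would leave the planned escalation untouched. Several of the tables are titled as recommended or suggested. The PPES table allows more conservative management at the investigator's discretion, and 9.5 lets the skin algorithm be used for diarrhea. A definition of SDRT may also stand in the schema that 16.1 mentions, which was not in the text available for this review.

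Some of this stands. The absence of a definition can be claimed only for the available text, and the intended reading may be benign. But no section states it, 8.0 asks for strict adherence, and the discretion attaches to PPES and diarrhea, not to fatigue, weight loss, rash or anorexia.

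A reader might go further and infer that Arm B is governed by the graded tables alone, so that Arm A has a reduction route that Arm B lacks and the comparison is confounded. The documents do not support that:

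- No section says that the graded tables alone govern Arm B. Section 8.3 names no arm, 8.34 refers to the tables of both 8.1 and 8.2, and the intolerable-toxicity sentence itself points to the Arm B table.
- Escalation and de-escalation driven by toxicity are part of the Arm A strategy as 1.1 describes it. They belong to the intervention and do not confound it.
- Grade 3 fatigue at 120 mg is not an example of conflicting doses. Table 8.31 delays and then drops one level, to 80 mg; 8.1 also arrives at 80 mg. It is silent on a hold but does not forbid one.

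**Conclusion.** The concern holds as an internal contradiction in the dose rules during the primary endpoint window. It is more than missing detail: at 120 mg a site reading the text literally cannot satisfy both 8.1 and the 8.3 tables, and at 80 mg the readings differ on whether the patient stays on treatment. Arm A therefore cannot be applied uniformly as written.

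The consequence for the A versus B result is possible but not shown. Its size is unknown, and it could go either way: an extra reduction route could keep patients on treatment, while 8.12 could remove Arm A patients who fail at 80 mg. It would be tempting to express the effect as a share of the 18-point target, but any such share rests on an assumed number of patients with no source in the documents.

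The verdict assumes a literal reading of the tables and that SDRT is not defined in the schema. If it is defined there, the missing-criterion point falls, but conflicts 1 and 3 and the missing outcome at 120 mg remain.

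**What to change.** Reconcile 1.1, 8.0, 8.1, 8.2 and the tables of 8.3 in one amendment, so that:

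- each event at each dose level gives one action, including at 80 mg and 120 mg in Arm A;
- SDRT is tied to stated criteria;
- the intolerable-toxicity sentence, and every other trigger, states which arm or arms it covers and how it relates to the Grade 0-2 row of Table 8.31;
- the text says which section prevails where two could apply.

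The clinical content of each rule is for the sponsor to choose; the review asks only that the passages agree. The cost is a wording amendment and a site memo, with somewhat less investigator latitude. No extra patients, visits or data are needed.

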8.2 Arm B Regorafenib Dose Levels (Based on Adverse Events in **Tables 8.3.**)

Dose Level	Drug	Dose
0*	Regorafenib	160 mg daily, Four 40-mg tablets
-1	Regorafenib	120 mg daily, Three 40-mg tablets
-2	Regorafenib	80 mg daily, Two 40-mg tablets

* Dose level 0 refers to the starting dose.

- 8.21 After week 8, if toxicities have resolved to \leq Grade 0-1, re-escalation is allowed 40 mg at a time every 4 weeks to a maximum of 160 mg and at the discretion of the treating investigator.

- 8.22 Patients with dose reductions below 80 mg should go off treatment and go to event monitoring.

If a subject experiences more than one toxicity, dose reduction should be according to the toxicity with the highest grade.

In the case of two or more toxicities of the same grade, the investigator may dose reduce according to that deemed most causally related to study treatment.

8.3 Regorafenib Dose Modifications

Table 8.31 Recommended dose modification for toxicities except hand-foot-skin reaction, hypertension and ALT/AST/bilirubin			
NCI-CTCAE v4.0^a	Dose Interruption	Dose Modification^b	Dose for Subsequent Cycles
Grade 0-2	Treat on time	No change	
Grade 3	Delay until \leq Grade 2 ^c	Reduce by 1 dose level	If toxicity remains < Grade 2, dose re-escalation can be considered at the discretion of the treating investigator. If dose is re-escalated and toxicity (\geq Grade 3) recurs, institute permanent dose reduction.
Grade 4	Delay until \leq Grade 2 ^c	Reduce by 1 dose level. Permanent discontinuation can be considered at treating investigator's discretion.	
a. NCI-CTCAE = National Cancer Institute - Common Terminology Criteria for Adverse Events, version 4.0 b. Excludes alopecia, non-refractory nausea/vomiting, lymphocyte count decreased, non-refractory hypersensitivity and nonclinical and asymptomatic laboratory abnormalities. c. If no recovery after a 4 week delay*, treatment should be permanently discontinued unless subject is deriving clinical benefit. * Modify according to study specific cycle length			

If greater than 2 dose level reductions are required, regorafenib will be discontinued and the rest of the study follow up may be continued. The following tables outline dose adjustments for toxicities related to regorafenib except hand-foot skin reaction, hypertension and liver function test abnormalities.

The table above outlines dose adjustments for hematologic and non-hematologic toxicities related to regorafenib except PPES and hypertension. In addition to these recommended dose modifications, subjects who develop diarrhea, mucositis, anorexia or other events predisposing to fluid loss or inadequate fluid intake should be carefully monitored and rehydrated as clinically necessary. This is in order to minimize the risk of postural hypotension and renal failure.

	Grade 1	Grade 2	Grade 3
NCI-CTCAE v4.0 Palmar-plantar erythrodysesthesia syndrome	Minimal skin changes or dermatitis (e.g., erythema, edema, or hyperkeratosis) without pain	Skin changes (e.g., peeling, blisters, bleeding, edema, or hyperkeratosis) with pain	Severe skin changes (e.g., peeling, blisters, bleeding, edema, or hyperkeratosis) with pain
Further description / examples of skin changes	Numbness, dysesthesia / paresthesia tingling, painless swelling, or erythema of the hands and/or feet	Painful erythema and swelling of the hands and/or feet	Moist desquamation, ulceration, blistering, or severe pain of the hands and/or feet
Effect on activities	Does not disrupt normal activities	Limiting instrumental activities of daily life (e.g., preparing meals, shopping for groceries or clothes, using the telephone, managing money)	Limiting self-care activities of daily life (e.g., bathing, dressing and undressing, feeding self, using the toilet, taking medications) and not bedridden
a. Palmer-plantar erythrodysesthesia syndrome is a disorder characterized by redness, marked discomfort, swelling, and tingling in the palms of hands or the soles of the feet.			

Grade of event (NCI-CTCAE v4.0)	Occurrence	Suggested Dose Modification
Grade 1	Any	Maintain dose level and immediately institute supportive measures for symptomatic relief
Grade 2	1 st occurrence	Consider decreasing dose by one dose level and immediately institute supportive measures. If no improvement, interrupt therapy for a minimum of 7 days, until toxicity resolves to Grade 0-1 ^{b,d}
	No improvement within 7 days or 2 nd occurrence	Interrupt therapy until toxicity resolves to Grade 0-1. When resuming treatment, treat at reduced dose level ^b
	3 rd occurrence	Interrupt therapy until toxicity resolves to Grade 0-1. When resuming treatment, decrease dose by one dose level. ^{b,d}
	4 th occurrence	Discontinue therapy
Grade 3	1 st occurrence	Institute supportive measures immediately. Interrupt therapy for a minimum of 7 days until toxicity resolves to Grade 0-1. ^c When resuming treatment, decrease dose by one dose level. ^{b,d}
	2 nd occurrence	Institute supportive measures immediately. Interrupt therapy for a minimum of 7 days until toxicity resolves to Grade 0-1. ^c When resuming treatment, decrease dose by one additional dose level. ^{b,d}
	3 rd occurrence	Discontinue treatment permanently.
a. More conservative management is allowed if judged medically appropriate by the investigator. b. If toxicity returns to Grade 0-1 after dose reduction, dose re-escalation is not permitted. c. If there is no recovery after a 4-week delay, treatment with regorafenib will be discontinued permanently. d. Subjects requiring > 2 dose reductions should go off protocol therapy. e. The maximum daily dose is 160 mg. f. Refer to Section 9.0 for management strategies for Palmer-plantar erythrodysesthesia syndrome reactions.		

